13.3. Recording and Grading Adverse Events for Severity

Adverse events spontaneously reported by the participant and/or in response to an open question from the study personnel or revealed by observation will be recorded during the study at the clinical site. The AE term should be reported in standard medical terminology when possible. For each AE, the investigator will evaluate and report the date of onset, date of resolution, severity, relatedness, action

taken, serious outcome (if applicable), and whether or not it caused the patient to discontinue the study. Each AE will be graded for severity using the applicable DAIDS tables for grading the severity of adverse events (see Table 8), which can also be found at <http://rsc.tech-res.com/safetyandpharmacovigilance/>.

Table 8: Grading the Severity of Adverse Events

Adult and Pediatric AEs	http://rsc.tech-res.com/Document/safetyandpharmacovigilance/DAIDS_AE_Grading_Table_v2_NOV2014.pdf
Female Genital AEs	http://rsc.tech-res.com/Document/safetyandpharmacovigilance/Addendum_1_Female_Genital_Grading_Table_v1_Nov_2007.pdf
Rectal Grading Table	http://rcc.tech-res.com/docs/default-source/safety/rectal-tox-table-updates-05-11-2012.pdf?sfvrsn=6

For clinical AEs NOT identified in the DAIDS AE Grading Tables, the following scale (as listed in the DAIDS Table for Grading the Severity of Adult and Pediatric AEs) should be used to grade severity:

- Mild: Symptoms causing no or minimal interference with usual social and functional activities
- Moderate: Symptoms causing greater than minimal interference with usual social and functional activities
- Severe: Symptoms causing inability to perform usual social and functional activities
- Potentially Life-Threatening: Symptoms causing inability to perform basic self-care functions OR medical or operative intervention indicated to prevent permanent impairment, persistent disability, or death

It is important to distinguish between serious and severe AEs. Severity is a measure of intensity whereas seriousness is defined by the criteria under Section 13.1.3. An AE of severe intensity may not necessarily be considered serious.

Participants must be protected from pregnancy to participate in the study. Should a pregnancy occur after baseline sampling, it must be reported as soon as possible to the study investigators. The participant will be discontinued from the study and appropriate exit procedures will be followed. Note that pregnancy in itself is not regarded as an AE. If the participant has been exposed to study product, the course of the pregnancy should be followed until it has an outcome (e.g., spontaneous miscarriage, elective termination, normal birth, congenital abnormality). If the participant seeks care outside the site, every effort should be made to obtain her consent for the site to receive a copy of her medical records related to the pregnancy, its outcome and the health of the neonate, if applicable.

Reports of congenital abnormalities/birth defects are SAEs. Spontaneous miscarriages should be reported and handled as SAEs. Elective abortions without complications should not be reported as AEs.

13.4. Reporting Serious Adverse Events

Any SAE, including those listed in the protocol or package insert must be reported to the EVMS IRB within 72 hours of discovery. If there is any question whether the event meets the criteria for “serious” it should be reported anyway. In addition, a completed SAE form must be filled out as soon as possible. The investigator must complete, sign and date the SAE pages, verifying the accuracy of the information recorded on the SAE pages and the corresponding source documents.

Additional follow-up information, if required or available, should all be sent to the EVMS IRB within one business day of receipt and this should be completed on an SAE form and placed with the original SAE information and kept with the appropriate section of the study database and/or study file.

The investigator will notify the EVMS IRB of any unexpected fatal or life-threatening suspected adverse reactions as soon as possible, but in no case later than 7 calendar days after she initially receives the information.

The site will promptly investigate and follow up on all safety information it receives, with the cooperation of the investigator.

The investigator is responsible for complying with IRB requirements for AE reporting.

13.5. Temporary Product Hold/Permanent Discontinuation in Response to Adverse Events

13.5.1. Grade 1 or 2

In general, a participant who develops a Grade 1 or 2 AE, regardless of relationship to study product, may continue product use. If the PI/designee opts to temporarily hold study product, reasons for product hold must be documented in the study source documents.

Follow-up testing for Grade 2 laboratory test results should be performed at scheduled study visits, as clinically relevant. More frequent testing may be performed at any time if required to properly monitor and/or manage participant safety, at the discretion of the PI/designee.

13.5.2. Grade 3 or 4

A participant who develops a Grade 3 or a Grade 4 AE that is product-related should have the product temporarily withheld. If a participant develops a Grade 3 or Grade 4 AE that is not product-related, the PI/designee may temporarily withhold product. In either case, the PI/designee must continue the temporary product hold until resolution of the AE. If product use is resumed and the same AE recurs at the same (or worse) grade level at any time during the study, study product must then be permanently discontinued.

14. STATISTICS

14.1. Sample Size Justification

Sample size is based on feasibility rather than statistical considerations; thus, analysis will be primarily descriptive and graphical. Participant flowchart (e.g. number screened, number with genital sampling) will be provided.

14.2. General Statistical Issues

All attempts will be made to avoid missing data. However, missing values will remain as missing, i.e., no attempt will be made to impute. In general, only observed values will be used in data analyses and presentations.

14.3. Analysis Populations

The population includes healthy, non-pregnant, HIV negative women. The analysis population will include all participants who undergo baseline genital/rectal sampling.

The Full Analysis Set (FAS) will consist of all subjects who are randomized and have at least one post-baseline assessment. The FAS will be used to summarize study disposition, baseline characteristics, and all non-safety endpoints.

Evaluation of safety endpoints will be conducted using the Treated Population (TP), consisting of women with at least one dose of product use. If all subjects in the TP have at least one post-baseline assessment, then the TP will be identical to the FAS.

All populations will be defined based on the adherence regimen assigned (HA versus LA).

Additional populations or refinements to these definitions, if needed due to unanticipated circumstances, will be described in the SAP or statistical report.

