5.2.2. Secondary Objectives

- Compare urine TFV concentration measured by the aptasensor with those values quantitated by LC-MS/MS to determine agreement between the two methodologies, sensitivity, specificity, NPV, and PPV
- Determine if the TFV aptasensor can detect differences in the urine concentrations of TFV between high and low adherence dosing regimens and whether these levels correlate with adherence
- Compare vaginal fluid TFV concentrations measured by the aptasensor with preclinical determinations of the range of detectable TFV levels and the aptasensor's limit of detection
- Determine if differences in adherence dosing regimens can be correlated to differences in vaginal fluid TFV levels

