9.3. Treatment Compliance

Treatment compliance will be evaluated by directly observed therapy (in-clinic dosing) at visits 2, 3 and 4, as appropriate to the participant’s dosing regimen, participant report and returned tablet count.

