14.4. Statistical Analysis

Sample size is based on feasibility rather than statistical considerations; thus, analysis will be primarily descriptive. Participant flowchart (e.g. number screened, number with sampling) will be provided. All populations will be defined based on the adherence regimen.

Evaluation of Study Objectives: Study objectives will be evaluated by clinical review of descriptive summaries and graphical displays.

Primary analysis of this study will evaluate the performance of the TFV aptasensor by comparing its measurements of the concentrations of TFV in clinical samples from all women with those values obtained from LC-MS/MS. Correlation and agreement between the TFV levels measured by the aptasensor and LC-MS/MS will be analyzed using scatterplot and linear regression. Continuous variables will be compared between values measured with the aptasensor versus LC-MS/MS using paired comparisons. From this comparison, sensitivity, specificity, NPV, and PPV of the aptasensor will also be determined. Confidence intervals will be calculated to assess precision and margin of error of those

measures. Using the 14 baseline pre-dose samples, each woman will be her own control, and these pre-dose samples will be used for the assessment of specificity and NPV.

The secondary analysis of this study will evaluate whether the aptasensor can detect differences in TFV levels between the two independent cohorts of women taking TDF/FTC at different dosing regimens representing high (7 pills/week) and low adherence (3 pills/week). We will compare the two independent cohorts using an independent samples t test for normally distributed data or a Wilcoxon-Mann-Whitney test for non-parametric data. TFV concentrations from the LA and HA cohorts will be characterized using descriptive statistics (mean, median, interquartile range, minimum and maximum). The values will be compared between the high adherence and low adherence groups as well as comparing the mean difference between groups generated by the aptasensor to that difference generated by LC-MS/ MS. Distributions will be checked to determine normality so as to determine the appropriate statistical test.

Descriptive Statistics: Categorical variables will be summarized by frequencies and percentages. Continuous variables will be summarized by means, standard deviations, medians, quartiles, minima and maxima.

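### The HA-LA contrast is analysed only by assigned regimen, so missed or held doses at Visits 4 and 5 can distort it in both assays, and the dosing records collected are used in no analysis

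*Combined protocol and SAP*

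**What the plan says.** Section 14.3 defines the Full Analysis Set (FAS) as randomized women with at least one post-baseline assessment, and adds: "The FAS will be used to summarize study disposition, baseline characteristics, and all non-safety endpoints". It then says: "All populations will be defined based on the adherence regimen assigned (HA versus LA". There is no per-protocol or as-taken set and no compliance threshold. The one opening is: "Additional populations or refinements to these definitions, if needed due to unanticipated circumstances, will be described in the SAP or statistical report".

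Section 14.4 compares HA with LA by a t test or a Wilcoxon-Mann-Whitney test, and sets the aptasensor's group difference against the LC-MS/MS group difference. It calls this the secondary analysis, although Section 5.2.1 lists the plasma contrast as a primary objective. Section 5.2.2 asks about HA-LA differences in urine and "whether these levels correlate with adherence", and has a similar objective for vaginal fluid.

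Dosing information is collected. Section 9.3 names observed in-clinic dosing, "participant report and returned tablet count"; Section 6.1 adds text-message confirmations; Section 10.6 requires doses taken to be recorded. Section 13.5 foresees holds: "If the PI/designee opts to temporarily hold study product, reasons for product hold must be documented". Section 14 uses none of this.

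**The concern.** In this study the regimen stands in for a level of adherence. If a woman assigned to HA does not take her doses, her samples no longer represent high adherence, but the HA-LA comparison still counts them as such. A small contrast could then mean that the two regimens give overlapping concentrations, or only that some women did not follow their regimen. The plan has no analysis that separates the two. At stake are a primary objective in plasma, the matching objectives in urine and vaginal fluid, and the objective on correlation with adherence, which a two-group test by assignment answers only if adherence means the assigned regimen.

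**Working it through.** The plan gives no power, effect size or SD (Section 14.1 bases sample size on feasibility), so it has no figure of its own to reproduce.

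**Inputs from the documents**
- 7 HA and 7 LA women planned (Table 3, Section 7.3.2).
- HA: 14 doses, of which those at Visits 2, 3 and 4 are observed (Table 6, Sections 8.3 and 10.5). Home doses: 14 − 3 = 11, unless a woman chooses to come in.
- LA: 6 doses, of which those at Visits 2 and 4 are observed in the example schedule (Table 7). Home doses: 6 − 2 = 4.
- In Table 6, the five HA doses between Visits 3 and 4 (doses 3 to 7) and the six between Visits 4 and 5 (doses 9 to 14) are all at home.
- At Visits 4 and 5, LA women are sampled three days after their last dose (Day 5 to Day 8, Day 12 to Day 15) and HA women one day after. An HA woman who misses Saturday and Sunday has the LA interval since last dose, though not necessarily the LA level.

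**Visit 3.** The sample is due 24 to 28 hours after the first dose (Section 15.2). By then each arm has had one dose, observed in clinic, so mislabelling cannot arise.

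**Dilution at Visits 4 and 5.** Let the true mean levels be μH and μL, and let k of the 7 HA women have LA-like levels. The expected difference is [(7 − k)μH + kμL]/7 − μL = (7 − k)/7 × (μH − μL), a loss of k/7: 1/7 = 14%, 2/7 = 29%, 3/7 = 43%. It is the same for both assays, because the concentration itself has changed. Missed doses in LA lower μL and move the difference the other way.

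**Chance of p<0.05.** Assumptions, not in the documents: normal data, two-sided 0.05, a sensor without error, and a true gap of d within-arm SDs. Simulation, 10,000 trials per cell, 7 versus 7, t test / exact Mann-Whitney:

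| k | d = 1 | d = 2 | d = 3 | d = 4 |
|---|---|---|---|---|
| 0 | 40% / 34% | 92% / 88% | >99% / >99% | 100% / 100% |
| 1 | 30% / 24% | 76% / 69% | 97% / 94% | >99% / >99% |
| 2 | 20% / 16% | 52% / 42% | 79% / 60% | 93% / 65% |
| 3 | 14% / 11% | 32% / 24% | 49% / 31% | 62% / 33% |

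Leaving out the k women gives, at d = 2, 86% / 83% for k = 2 and 81% / 75% for k = 3; at d = 3, >99% / 99% and 99% / 97%. This is a best case, since it assumes the records identify these women without error.

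**How likely is k of 2 or more?** The documents give no rate. If each HA woman independently has probability 5%, 10%, 20% or 30% of an LA-like level, the binomial chance of at least 2 of 7 is 4%, 15%, 42% or 67%.

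**The case against.** The strongest reply is that regimen is not the plan's reference standard. The primary analysis works by "comparing its measurements of the concentrations of TFV in clinical samples from all women with those values obtained from LC-MS/MS". Sensitivity, specificity, PPV and NPV come from that comparison, and for baseline samples "these pre-dose samples will be used for the assessment of specificity and NPV". A missed dose changes the true concentration for both assays, so it creates no sensor error there. The regimen contrast also has a control: a perfect sensor reproduces the LC-MS/MS difference exactly, however many women deviate. All of this stands. A reader might infer that every non-safety result is compromised, or that a perfect sensor would appear to fail. The documents support neither.

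A reader might also infer that a perfect sensor could detect HA in at most 6/7 (86%) or 5/7 (71%) of women. Section 14.4 plans no classification of women as HA or LA, so those caps apply to no planned result. Nor does non-adherence always bias towards zero, given the opposite effect of missed LA doses.

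What does not stand is that the LC-MS/MS contrast settles the matter. It shows whether the assays agree; if both contrasts are small, it cannot say whether missed doses or true overlap between regimens is the reason. For vaginal fluid, the specific objective in Section 5.2.2 names preclinical ranges, not LC-MS/MS, as comparator. The opening in Section 14.3 is for unanticipated circumstances, whereas missed and held doses are anticipated by the reminders, tablet counts and hold rules.

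It is also fair to say that the documents often use adherence to mean the assigned regimen, that reminders, observed doses and withdrawal for serious non-compliance (Section 7.3.1) reduce the problem, and that this is a descriptive pilot with no decision rule. These points limit the weight of the concern without removing it.

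**Conclusion.** The point holds for the HA-LA contrast at Visits 4 and 5, and only there. Following the plan as written can understate regimen discrimination for both assays when HA women deviate, or overstate it when LA women miss doses. The k/7 loss assumes 7 women in the HA arm (simple randomization may give another number) and deviators whose levels match the LA mean; a woman who skips one early dose but takes the last one need not look like LA. One such woman does not hide a gap of 3 SD or more. Two or three can hide a real difference: at an assumed 2 SD gap, the chance of p<0.05 by t test falls from about 92% to 52% or 32%. The gap, the SD and the rate of deviation are all assumptions. The change is worth making because it costs little and answers an objective that the present analysis leaves partly open.

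**What to change.** Keep the assigned-regimen FAS analysis as it is. Add to Section 14.4, before the analysts are unblinded, two supportive analyses for Visits 4 and 5, for each assay and fluid measured, shown beside the assigned-regimen result:

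- (a) the HA-LA comparison limited to women whose tablet count and dose confirmations match the assigned doses since the last visit, with the matching rule stated;
- (b) log TFV against the recorded number of doses taken in the previous 7 days, with days since last dose described where recorded. This also addresses the objective on correlation with adherence.

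Visit 3 needs neither.

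The cost is analysis wording and some data handling; the data are already to be collected. The limits should be stated with the results. Both analyses rest partly on self-report, which Section 4 itself calls unreliable. Section 15.2 requires exact times only for in-clinic doses, so time since the last home dose may be incomplete. Analysis (a) selects after randomization among about 14 women. Both are therefore descriptive and do not replace the assigned-regimen result.

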14.4. Statistical Analysis

Sample size is based on feasibility rather than statistical considerations; thus, analysis will be primarily descriptive. Participant flowchart (e.g. number screened, number with sampling) will be provided. All populations will be defined based on the adherence regimen.

Evaluation of Study Objectives: Study objectives will be evaluated by clinical review of descriptive summaries and graphical displays.

Primary analysis of this study will evaluate the performance of the TFV aptasensor by comparing its measurements of the concentrations of TFV in clinical samples from all women with those values obtained from LC-MS/MS. Correlation and agreement between the TFV levels measured by the aptasensor and LC-MS/MS will be analyzed using scatterplot and linear regression. Continuous variables will be compared between values measured with the aptasensor versus LC-MS/MS using paired comparisons. From this comparison, sensitivity, specificity, NPV, and PPV of the aptasensor will also be determined. Confidence intervals will be calculated to assess precision and margin of error of those

measures. Using the 14 baseline pre-dose samples, each woman will be her own control, and these pre-dose samples will be used for the assessment of specificity and NPV.

The secondary analysis of this study will evaluate whether the aptasensor can detect differences in TFV levels between the two independent cohorts of women taking TDF/FTC at different dosing regimens representing high (7 pills/week) and low adherence (3 pills/week). We will compare the two independent cohorts using an independent samples t test for normally distributed data or a Wilcoxon-Mann-Whitney test for non-parametric data. TFV concentrations from the LA and HA cohorts will be characterized using descriptive statistics (mean, median, interquartile range, minimum and maximum). The values will be compared between the high adherence and low adherence groups as well as comparing the mean difference between groups generated by the aptasensor to that difference generated by LC-MS/ MS. Distributions will be checked to determine normality so as to determine the appropriate statistical test.

Descriptive Statistics: Categorical variables will be summarized by frequencies and percentages. Continuous variables will be summarized by means, standard deviations, medians, quartiles, minima and maxima.

Control of Type I Error: This pilot study is descriptive in nature. P-values and confidence intervals around estimates of treatment differences will not be adjusted for multiplicity and are descriptive in nature. These statistics will be provided to guide clinical judgment; caution must be used as these statistics will not have a controlled Type I error.

Definition of Baseline: For both adherence regimens baseline is defined as the Visit 2 pre-dose measurement.

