5.2.1. Primary Objectives

- Compare plasma TFV concentrations measured by the aptasensor with those values quantitated by LC-MS/MS to determine agreement between the two methodologies, sensitivity, specificity, NPV, and PPV
- Determine if the TFV aptasensor can detect differences in the plasma TFV concentrations between high and low adherence dosing regimens and compare the mean difference to the difference calculated from values generated by LC-MS/MS

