5.3. Endpoints

5.3.1. Primary Endpoint

- TFV concentrations in *plasma* at baseline (pre-dose), 24 hours, 7 days and 14 days after dosing

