7.3.2. Target Enrollment

Participants who initiate product use but discontinue the study prior to completion may not re-enroll. Participants will be screened and enrolled so that approximately 14 women (7 per adherence cohort) complete all study visits.

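### As written, the agreement analysis in Section 14.4 is not restricted to post-dose samples, so 14 drug-free pairs among 56 may raise the correlation and shrink the mean difference

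*Combined protocol and SAP*

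**What the plan says.** The first primary objective (Section 5.2.1) is to "Compare plasma TFV concentrations measured by the aptasensor with those values quantitated by LC-MS/MS to determine agreement between the two methodologies". The primary endpoint (Section 5.3.1) is plasma TFV "at baseline (pre-dose), 24 hours, 7 days and 14 days after dosing", so baseline is one of its four time points.

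Section 14.4 carries out the comparison in "comparing its measurements of the concentrations of TFV in clinical samples from all women with those values obtained from LC-MS/MS". The methods are: "Correlation and agreement between the TFV levels measured by the aptasensor and LC-MS/MS will be analyzed using scatterplot and linear regression", and "Continuous variables will be compared between values measured with the aptasensor versus LC-MS/MS using paired comparisons". No visit is named or excluded. The accuracy measures come from the same exercise: "From this comparison, sensitivity, specificity, NPV, and PPV of the aptasensor will also be determined". The section continues "Using the 14 baseline pre-dose samples, each woman will be her own control", and assigns those samples to specificity and NPV without saying that this is their only use.

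Baseline samples are taken before the first pill (Section 8.2), and antiretroviral use in the previous two weeks is an exclusion (Section 7.2), so they should be essentially drug-free. The Full Analysis Set is defined by participant, not by sample (Section 14.3). Section 14.2 deals with missing values only. The lower limit of quantification appears in the abbreviation list, but with no value and no handling rule.

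**The concern.** Pairs in which both methods read about zero form a cluster at the origin. They show whether the sensor is quiet when no drug is present. They do not show how closely it tracks LC-MS/MS when drug is present. Pooled with post-dose pairs, they widen the concentration range, which tends to raise r, and they add near-zero differences to the paired comparison.

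The trial asks more than whether the sensor detects drug. It asks about agreement on concentration, and about telling low from high adherence. With no hypothesis test or agreement threshold, the descriptive r and mean difference are themselves the result, and the synopsis says the statistics will guide further development of the sensor. A pooled figure could make quantitative performance look better than the drug-containing samples support.

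**Working it through.** **Inputs from the documents.** The target is that "approximately 14 women (7 per adherence cohort) complete all study visits" (Section 7.3.2). There are four plasma time points per woman, one of them pre-dose (Section 5.3.1).

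**The plan's own figure.** (7 + 7) women × 1 pre-dose sample = 14, which matches Section 14.4. Then 14 × 4 = 56 plasma pairs, of which 14 × 3 = 42 are post-dose. The pre-dose share is 14/56 = 25%.

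**Assumptions.** The documents give no concentrations, spread or sensor error. Set the post-dose LC-MS/MS mean to 1 with CV c. Let the post-dose sensor reading be the LC-MS/MS value plus mean-zero error with variance t². Let both methods read zero before dosing. A post-dose correlation r implies t² = c²(1 − r²)/r². The post-dose share is p = 0.75, so p(1 − p) = 0.1875.

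**Correlation.** The pooled variance of LC-MS/MS is V = 0.75c² + 0.1875, and pooled r = √[V/(V + 0.75t²)]. At c = 0.5 and r = 0.50, V = 0.375 and t² = 0.75, so pooled r = √(0.375/0.9375) = 0.63. The same formula gives:

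| Post-dose CV | r = 0.30 | r = 0.50 | r = 0.70 | r = 0.90 |
|---|---|---|---|---|
| 50% | 0.41 | 0.63 | 0.81 | 0.95 |
| 100% | 0.33 | 0.54 | 0.74 | 0.92 |

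**No post-dose correlation.** If the sensor has the same mean and CV as LC-MS/MS but is unrelated to it after dosing, pooled r = 0.1875/(0.75c² + 0.1875):
- CV 40%: 0.1875/0.3075 = 0.61
- CV 50%: 0.1875/0.375 = 0.50
- CV 100%: 0.1875/0.9375 = 0.20

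**Mean difference.** With post-dose mean difference b, the pooled value is (42b + 14 × 0)/56 = 0.75b.

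**Scatter.** With k = b divided by the post-dose SD of differences, the ratio of pooled to post-dose SD is √(0.75 + 0.1875k²). This is 0.87 at k = 0, 0.89 at k = 0.5, 0.97 at k = 1 and 1.22 at k = 2. Pooling enlarges the SD once k² > 0.25/0.1875, that is, above about k = 1.15.

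**Where the effects weaken or vanish.**
- *Blanks as noisy as post-dose samples.* Pooled r = √[V/(V + t²)], which exceeds r only if V > c², that is, c < √0.75 = 0.87. From r = 0.50 it becomes 0.58 at CV 50% but 0.49 at CV 100%.
- *Constant sensor offset.* The offset is also present in the blanks. In 4,000 simulated trials with an offset of 0.2 of the mean post-dose level, the median mean difference was 0.201 post-dose and 0.201 pooled.
- *Proportional bias.* If the post-dose readings scatter about a line through the origin, blanks at (0, 0) lie on that line. The regression slope is therefore the same with or without them; only the mean difference shrinks.
- *Paired t statistic.* Treating pairs as independent, for illustration, at k = 0.5 it is 0.5√42 = 3.24 post-dose and 0.375√56/0.893 = 3.14 pooled, which is almost unchanged.
- *Values below quantification dropped.* The 14 pairs leave the analysis and nothing changes.

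**The case against.** The strongest reply is that the plan never says it pools all samples. It refers to all women, and the one role it names for the pre-dose samples is specificity and NPV. It is right that inclusion is an inference. It is still the natural reading: baseline belongs to the primary endpoint, no visit is excluded, and specificity, which rests on these samples, is drawn from the same comparison.

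Three stronger readings are tempting, and the documents do not support them.
- A reader might infer that any sensor bias would be reported a quarter too small. That holds only for the mean difference, and only if the sensor reads zero on blanks, which the specificity analysis is there to test. Blanks also carry real information on intercept and background.
- A reader might infer that a pure on/off sensor would pass. The planned scatterplot would show two clusters, and the second primary objective compares the sensor's high-versus-low adherence difference with that of LC-MS/MS. With assumed levels of 60/100/100 (high) and 60/20/20 (low), LC-MS/MS would show 86.7 − 33.3 = 53.3, and such a sensor about 0.
- A reader might infer that the plan leaves plasma undistinguished from the other fluids. Section 14.4 names no fluid, but Sections 5.2 and 5.3 already make plasma primary and urine and vaginal fluid secondary.

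It also stands that this is a feasibility-sized descriptive pilot (Section 14.1) with no agreement threshold. What survives is that the pooled r and mean difference would, in the ordinary case, look better than the post-dose data.

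**Conclusion.** The point holds in a conditional form. On the natural reading of Sections 5.3.1 and 14.4, a quarter of the planned plasma pairs in the agreement analysis are drug-free. If both methods read near zero in those pairs, r rises (0.50 to about 0.63 at an assumed CV of 50%, or 0.54 at 100%), and the mean paired difference falls to 0.75 of its post-dose value. The SD of differences falls by about 3% to 13% for a bias of up to one SD.

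The count of 14 in 56 comes from the documents and assumes complete sampling. The CVs, correlations and sensor behaviour are assumptions. Whether the effect arises at all depends partly on how values below quantification are handled, which the plan leaves open. The 56-pair count is firmest for plasma, because the specific vaginal-fluid objective compares sensor readings with preclinical ranges and the detection limit.

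Severity is minor to moderate. No test or threshold turns on the result, but it is the reported answer to the first primary objective.

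**What to change.** Amend Section 14.4 and the statistical methods in the synopsis as follows:

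- Make the post-dose pairs the main agreement analysis (correlation, regression and paired differences), by fluid, with plasma primary.
- Do not drop a post-dose sample only because LC-MS/MS is below quantification. In the example low-adherence schedule (Table 7), Visits 4 and 5 fall on Days 8 and 15 and the preceding doses on Days 5 and 12, a gap of three days. Dropping such values could remove the low end of the range that the study needs. State how these values enter, and show results with and without them.
- Keep the pre-dose pairs for specificity and NPV as planned, and add a separate summary of the sensor's blank reading.
- Label any all-sample correlation or mean difference as supportive.

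The cost is a few sentences and no new data. The downside for the sponsor is that the reported r will probably be lower.
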